3.3 Exclusion Criteria

- 3.3.1 Patients diagnosed with another malignancy – unless following curative intent therapy, the patient has been disease free for at least 2 years and the probability of recurrence of the prior malignancy is < 5%. Patients with curatively treated early-stage squamous cell carcinoma of the skin, basal cell carcinoma of the skin, or cervical intraepithelial neoplasia (CIN) are eligible for this study.
- 3.3.2 Concurrent cancer therapy is not permitted.
- 3.3.3 Uncontrolled central nervous system (CNS) metastases, meningeal carcinomatosis, malignant seizures, or a disease that either causes or threatens neurologic compromise (e.g., unstable vertebral metastases).
- 3.3.4 History of ascites or pleural effusions, unless successfully treated.
- 3.3.5 Patients with an organ transplant, including those that have received an allogeneic bone marrow transplant.
- 3.3.6 Patients on immunosuppressive therapy including:
 - a) Systemic corticosteroid therapy for any reason, including replacement therapy for hypoadrenalinism. Patients receiving inhaled or topical corticosteroids may participate (if therapy is < 5 days and is limited to systemic steroids as antiemetics).
 - b) Patients receiving cyclosporine A, tacrolimus, or sirolimus are not eligible for this study.
- 3.3.7 Use of investigational agents within 4 weeks prior to study enrollment (within 6 weeks if the treatment was with a long-acting agent such as a monoclonal antibody).

- 3.3.8 Patients with moderate or severe cardiac disease:
- a) have the presence of cardiac disease, including a myocardial infarction within 6 months prior to study entry, unstable angina pectoris, New York Heart Association Class III/IV congestive heart failure, or uncontrolled hypertension.
 - b) have documented major electrocardiogram (ECG) abnormalities (not responding to medical treatments) at the investigator's discretion (for example, symptomatic or sustained atrial or ventricular arrhythmias, second- or third-degree atrio ventricular block, complete bundle branch block, ventricular hypertrophy, or recent myocardial infarction).
 - c) have major abnormalities documented by echocardiography (ECHO) with Doppler (for example, moderate or severe heart valve function defect and/or left ventricular ejection fraction <50%, evaluation based on the institutional lower limit of normal). For additional details, refer to ECHO protocol.
 - d) have predisposing conditions that are consistent with development of aneurysms of the ascending aorta or aortic stress (for example, family history of aneurysms, Marfan-Syndrome, bicuspid aortic valve, evidence of damage to the large vessels of the heart documented by computed tomography (CT) scan with contrast).
- 3.3.9 Troponin I above ULN,
- 3.3.10 Patients with a remote history of asthma or active mild asthma may participate.
- 3.3.11 Active infection, including unexplained fever (temperature > 38.5°C).
- 3.3.12 Systemic autoimmune disease (e.g., systemic lupus erythematosus, active rheumatoid arthritis, Marfan Syndrome, etc.).
- 3.3.13 A known allergy to any component of LY2157299.
- 3.3.14 Patients who, in the opinion of the Investigator, have significant medical or psychosocial problems that warrant exclusion. Examples of significant problems include, but are not limited to:
- a) Other serious non-malignancy-associated medical conditions that may be expected to limit life expectancy or significantly increase the risk of SAEs.

b) Any condition, psychiatric, substance abuse, or otherwise, that, in the opinion of the Investigator, would preclude informed consent, consistent follow-up, or compliance with any aspect of the study

3.3.15 Pregnant or nursing women, due to the unknown effects of LY2157299 on the developing fetus or newborn infant.

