2.2.3 Toxicology Studies

Eli Lilly and Company has performed toxicology studies in rodents and dogs. Details of each of these studies can be found in the Investigator Brochure.

In 6-month long-term nonclinical toxicity studies, daily dosing of LY2157299 resulted in dose-progressive incidence of vascular degeneration to the base of the aorta in dogs and rats. Vascular changes led to transmural aneurysms and mortality in mid-high dose-treated rats. Due to the possibility of aneurysm formation, patients with a history of or predisposition of developing aneurysms should not receive LY2157299. Subsequent cardiovascular function studies carried

out in dogs revealed that LY2157299 can cause a decrease in blood pressure and increases in heart rate and arterial pulse pressure, all reversible. There were no compound-attributable changes in QT intervals, arrhythmias, or altered waveforms noted. Because of the associated cardiac events in animal studies, patients on LY215799 undergo cardiac monitoring, including assessment of heart rate, blood pressure and cardiac functions. Regular monitoring of biomarkers for cardiac events, including troponin-I, B type natriuretic peptide and high sensitivity C-reactive protein is required..TGF- β is an important immunomodulator, hence, careful monitoring of immune functions and infection rates is important. Because LY2157299 inhibits TGF- β receptor type-1 kinase, an autoimmune reaction may occur. To date, no clinically significant immune reactions have been reported or observed up to doses of 300 mg/day in a 14 days-on / 14 days-off treatment regimen.

LY2157299 should not be administered to pregnant patients or all efforts should be made to prevent pregnancy due to TGF- β 's role in embryogenesis. Literature searches as well as treatment with LY2157299 in pregnant rats showed increased resorptions and alterations in fetal skeletal morphology at dose equivalents of 300 mg/day in humans.

LY2157299 does not demonstrate any direct bone marrow toxicity in either animal studies with continuous dosing for 6 months, nor in human colony-forming unit studies with human bone marrow progenitor cells. There have been 2 cases with drug-related severe thrombocytopenia and associated pan-cytopenia observed, but they cannot be explained at this juncture.

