4 REGISTRATION PROCEDURES

4.1 General Guidelines

All eligible patients who are referred to the Radiation Oncology or Medical Oncology Department at Weill Cornell Medicine for radiation will be offered the opportunity to participate in this experimental protocol. Treatment may commence once all mandatory pretreatment studies are documented, informed consent is obtained and the patient is approved according to the eligibility checklist. Eligibility will be determined by the investigators of the study.

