- Common Terminology Criteria for Adverse Events Grade 3 or 4 non-hematologic toxicity

Non-hematologic and hematologic toxicity must resolve to CTCAE Grade 0, 1, or baseline (with the exception of alopecia, fatigue, skin rash, nausea, vomiting, constipation, or diarrhea that can be controlled with treatment) before start of next cycle. If recovery is >29 days (Day 1 of the next cycle), patient must be withdrawn from study treatment.

If moderate or severe heart valve toxicities are observed, or the patient develops aneurysms of the great vessels of the heart, the patient must immediately be discontinued from the treatment and the toxicity reported to sponsor within 24 hours (see references on the ECHO assessment based on the Guidelines of the American and European Societies of Cardiac Echocardiography). If the patient develops new cardiovascular lesions in the chest, an MRI or CT with contrast of the abdomen should be performed to evaluate for development of abdominal vascular lesions. Exceptions to this rule must be approved by the IRBs and sponsor.

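### The one exclusion that names aneurysm, 3.3.8(d), is narrower than the statement in 2.2.3 of who should not receive the drug, and the two should be reconciled

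*Combined protocol and SAP*

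**What the plan says.** Section 2.2.3 (Toxicology Studies) reports that six months of daily dosing produced "vascular degeneration to the base of the aorta in dogs and rats", which went on to transmural aneurysms and deaths in rats at mid to high doses. It then concludes that "patients with a history of or predisposition of developing aneurysms should not receive LY2157299".

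In section 3.3, aneurysm is named once, in item 3.3.8(d). That item sits under the heading "Patients with moderate or severe cardiac disease" and excludes patients who "have predisposing conditions that are consistent with development of aneurysms of the ascending aorta or aortic stress". Its examples are "family history of aneurysms, Marfan-Syndrome, bicuspid aortic valve, evidence of damage to the large vessels of the heart", the last to be shown on contrast CT.

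Two other exclusions bear on the point without naming aneurysm. Item 3.3.3 covers, among other things, disease that causes or threatens neurologic compromise. Item 3.3.14(a) lets the investigator exclude a patient with "Other serious non-malignancy-associated medical conditions that may be expected to limit life expectancy or significantly increase the risk of SAEs".

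Under section 4.1, the investigators determine eligibility, and treatment may begin once pretreatment studies and consent are in place and "the patient is approved according to the eligibility checklist".

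**The concern.** The document describes the patients who should not be treated in two places, and the descriptions differ. The broader one is in the background section. The narrower one is in the criteria from which sites enrol. Where they differ, a site working through section 3.3 item by item could find no mandatory exclusion for a patient whom 2.2.3 says should not receive the drug.

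Vascular degeneration leading to aneurysm is a serious finding in the animal studies summarised in 2.2.3, and safety is a primary objective (1.1.1). A vascular event in a patient who met one description but not the other would be hard to interpret. The two centres, WCM and UCLA, could also read the same criterion differently.

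**Working it through.** The point rests on no rate, effect size or sample size, and the plan gives no figure to reproduce. The check is a side-by-side reading of 2.2.3 against every criterion in 3.1 to 3.3, the screening list in 5.2 and the on-study rules in 5.3.

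| Element | Section 2.2.3 | Section 3.3 |
|---|---|---|
| Patient's own history of aneurysm | Named | Not named in any item |
| Predisposition to aneurysm | Named | Named in 3.3.8(d) |
| Vascular site | No limit stated | Ascending aorta, or aortic stress (undefined) |
| Force | Should not receive the drug | 3.3.8(d) mandatory; 3.3.14(a) rests on the investigator's opinion |

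Step 1, history against predisposition. 2.2.3 names both. 3.3.8(d) names predisposing conditions only. Its examples include a family history of aneurysm but not the patient's own. Even a past aneurysm of the ascending aorta is not named in terms.

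Step 2, site. 2.2.3 states no vessel. 3.3.8(d) refers to the ascending aorta and then to aortic stress, which the protocol does not define. Its last example concerns the large vessels of the heart.

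Step 3, how far other wording closes the gap.
- Aortic aneurysm outside the ascending portion: aortic stress is not confined to the ascending aorta, and the examples in 3.3.8(d) are illustrative. An investigator could reasonably exclude here.
- Intracranial aneurysm: 3.3.3 could be read to cover it as a threat of neurologic compromise, although the items around it and the example given are oncological.
- Other non-aortic sites, such as an iliac aneurysm: no mandatory item clearly applies. 3.3.14(a) allows exclusion but does not require it.

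Step 4, imaging. Section 5.2 requires echocardiography, body PET/CT or CT, and brain MRI or contrast CT at baseline, so an aneurysm might be seen. No criterion states that such a finding, outside the scope of 3.3.8(d), leads to exclusion.

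Step 5, size. The documents give no prevalence of aneurysm in this population. Assuming 0 to 1 of the 28 planned patients, the share is 0/28 = 0% to 1/28 = 3.6%.

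**The case against.** The strongest reply is that the protocol, read as a whole, already covers nearly all such patients. 3.3.14(a) reaches conditions that raise the risk of serious events. A known aneurysm fits it naturally in a protocol that contains 2.2.3, and the investigators who apply it are the same people who determine eligibility under 4.1. If a relative's aneurysm shows predisposition, the patient's own surely does. The cardiac heading does not limit item (d), since family history and Marfan syndrome are not moderate or severe cardiac disease. The ascending-aorta focus also matches the animal lesion at the base of the aorta, so it may be deliberate.

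Much of this stands. It shows that a sensible investigator would often reach the result 2.2.3 calls for, and it disposes of any argument from the heading. It does not show that the criteria require that result. 2.2.3 is categorical, and a clause that depends on opinion does not carry it out. If the narrower scope is intended, the documents do not say so, and 2.2.3 is not limited in that way.

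Several stronger readings are tempting but unsupported:
- A reader might infer that a patient with an aneurysm elsewhere will pass the eligibility checklist. The checklist is not among the documents, so its content is unknown.
- A reader might infer that every aneurysm outside the ascending aorta is missed. Step 3 of the working shows otherwise.
- A reader might infer that the entry rule is the only protection. Section 5.3 also schedules echocardiography, repeats body PET/CT or CT at weeks 5 and 15 (for tumour measurement), and requires discontinuation if an aneurysm of the great vessels of the heart develops.
- A reader might take the instruction that "CT with contrast of the abdomen should be performed to evaluate for development of abdominal vascular lesions" as proof that pre-existing abdominal aneurysm was meant to bar entry. Section 5.3 calls for that imaging, by MRI or CT, only after a new cardiovascular lesion appears in the chest.

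**Conclusion.** The mismatch is real and has two parts: a personal history of aneurysm is in 2.2.3 but in no exclusion, and 3.3.8(d) limits the site where 2.2.3 does not. It is clearest for a personal history and for non-aortic sites; for other aortic and some intracranial aneurysms it is a matter of interpretation.

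The number of patients affected is probably very small. The figure of 0 to 1 of 28 is an assumption, and the documents cannot confirm or refute it. The possible severity is inferred from the rat findings, not from human data in the protocol. The conclusion also assumes that the checklist mirrors 3.2 and 3.3. It does not depend on which scope is right, because the current text states two. The point is a safety-related reconciliation of two named sections and does not affect the statistical design.

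**What to change.** Reconcile 2.2.3 and 3.3.8(d), and the matching line of the eligibility checklist, so that all name the same patients. The revised text should state explicitly whether a personal history of aneurysm is covered, and whether aneurysms outside the ascending aorta are covered. The term aortic stress should be defined or replaced. The sponsor and investigators decide the scope; if the narrower one is intended, 2.2.3 should say so and give the reason.

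The cost is a wording amendment and an updated checklist line, with no new procedure. The downside is possibly an occasional extra screen failure if the broader scope is chosen.

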4 REGISTRATION PROCEDURES

4.1 General Guidelines

All eligible patients who are referred to the Radiation Oncology or Medical Oncology Department at Weill Cornell Medicine for radiation will be offered the opportunity to participate in this experimental protocol. Treatment may commence once all mandatory pretreatment studies are documented, informed consent is obtained and the patient is approved according to the eligibility checklist. Eligibility will be determined by the investigators of the study.

4.2 Patient Registration Process

Before any protocol specific procedures can be carried out, investigators/staff will fully explain the details of the protocol, the study procedures and the aspects of patient privacy regarding research information. Patients will be provided a comprehensive explanation of the proposed treatment including the type of therapy, the rationale for treatment on the protocol, alternative treatments that are available, any known adverse events, the investigational nature of the study and the potential risks and benefits of the treatment. The informed consent document will meet all requirements of the Institutional Review Board (IRB). All subjects/patients are informed in the consent that participation or refusal to participate in the research study will not affect any of the clinical treatment or services to which they would otherwise be entitled.

The physicians who may obtain informed consent are listed on the title page of this protocol. The informed consent form will be signed by the participant and the registering physician. Once signed, a copy will be given to the patient and one will be maintained with the patient's medical record. Once eligibility is confirmed and informed consent is documented, the patient will be registered by the study coordinator/data manager.

IND # 126952

Protocol # 1505016222
Version Date 04/21/2017

Patients will be centrally registered with the Office of Billing Compliance. To register a patient, submit the following documents via the JIRA Registration Process:

- 1. Legible copy of the HRBAF**
- 2. First and last page of signed informed consent form**

Registration must be completed within 24 hours of the signing of informed consent.

5. TREATMENT PLAN

5.1 Investigational Agent or Device Administration

Enrolled patients will receive 300 mg/day of LY2157299. LY2157299 will be administered as an oral drug tablet.

The study drug will be administered orally on a 28-day cycle (1 cycle=28 days), every 2 weeks, or 14 days on / 14 days off. Blood samples will be obtained at baseline, and weeks 2, 6 and 15 for immune monitoring. Imaging by PET/CT or CT(Chest/Abdomen/Pelvis) will be performed at baseline, 5 weeks and 15 weeks. The chosen metastatic sites will receive conformal external beam radiation 7.5 Gy/fraction x 3, to a total of 22.5 Gy over the course of one week (on alternating days):

- lesion 1 will be irradiated at week 1 (RT starts 1 day after 1st dose of LY2157299),
- lesion 2 will be irradiated at week 5 (RT starts after 1stdose of the second cycle of LY2157299)

5.2 Pretreatment Evaluations

Screening and Baseline Evaluations/Procedures

These evaluations will be carefully reviewed to determine the patient's eligibility for the study (see study calendar, section 5.10).

1. Signed, written informed consent: Consent must be completed prior to performing any study-related procedures
2. Complete physical examination including height, weight and full skin exam.

3. Medical history: Detailed documentation of demographics, disease and treatment history with outcomes.
4. ECOG performance status assessment.
5. Concurrent medications.
6. Echo / Doppler.
7. Hematology: CBC with differential and platelet count and peripheral blood smear. Coagulation (PT/INR, PTT); Serum chemistries: Electrolytes (sodium, potassium, chloride, and bicarbonate), blood urea nitrogen (BUN), creatinine, glucose, and liver function tests (aspartate aminotransferase (AST) and/or alanine aminotransferase (ALT), alkaline phosphatase (ALP), total bilirubin, lactate dehydrogenase (LDH), and Troponin I..
8. Tumor measurement at baseline by PET/CT or CT(chest/abdomen/pelvis).
9. MRI or Brain CT with contrast is required at baseline
10. Stool fecal occult blood test of 2 consecutive samples: if patients have positive fecal occult blood, full GI workup will be conducted and patients will be excluded if active bleeding is detected.
11. LY2157299 Serum pregnancy test for women of childbearing age.

5.3 On-Study Evaluations

(See study calendar, section 5.10)

1. Physical exam: including complete skin evaluation and evaluation of oral mucosa prior to start of **each** RT cycle and **prior** to each LY2157299 administration.
2. Hematology: CBC with differential and platelet count and peripheral blood smear. PT/INR,PTT should be evaluated following multiple doses of LY2157299; Serum chemistries: Electrolytes (sodium, potassium, chloride, and bicarbonate), BUN, creatinine, glucose, and liver function tests (AST, ALT, ALP, total bilirubin, LDH, and Troponin I C). These will be carried out prior to start of each RT cycle and prior to each cycle of 2 weeks of BID LY2157299 administration.
3. ECHO/Doppler : Week 8 within 5 days prior to starting week 9 LY2157299 administration and Week 15
4. Study Special Tests: TGF β levels (at wk 1 day -1 and week 15 visit), immune evaluation at weeks 1 day -1, 2, 5 and 15 LY2157299 PK (pre- & after completion of drug cycle day 14 & at day 42).
5. Tumor measurement by PET/CT/ CT(chest/abdomen/pelvis) at weeks 5 and 15.
6. Adverse events evaluated and recorded using the NCI CTCAE version 4.0 throughout the treatment period (weeks 0-15).

To date, LY2157299 at the planned dose for this study is well tolerated in patients. If a toxicity is observed, a dose reduction may be considered based on the aggregate safety information of LY2157299, if other plausible reasons for a toxicity have been excluded.

Specifically, no bone marrow toxicities were detected in nonclinical toxicology studies; 1 toxicity was reported in a patient with glioblastoma in whom a Grade 4 thrombocytopenia was observed and this toxicity was potentially associated with administration of LY2157299 monotherapy. If a similar case occurs, the drug should be discontinued until platelet counts either return to Grade 1 or baseline.

If a patient experiences any of the following events that are considered possibly related to LY2157299 and not to study disease, LY2157299 will be omitted until the event resolves:

- Grade 4 Thrombocytopenia
- Grade 3 thrombocytopenia associated with bleeding
- Grade 4 Anemia
- absolute neutrophil count (ANC) $<0.5 \times 10^9/L$ for longer than 7 days, or ANC $<1.0 \times 10^9/L$ with a single temperature of $>101^{\circ}\text{F}/38.3^{\circ}\text{C}$ or a sustained temperature of $>100.4^{\circ}\text{F}/38^{\circ}\text{C}$ for more than 1 hour, or platelet count $<25,000 \times 10^9/L$
- Common Terminology Criteria for Adverse Events Grade 3 or 4 non-hematologic toxicity

Non-hematologic and hematologic toxicity must resolve to CTCAE Grade 0, 1, or baseline (with the exception of alopecia, fatigue, skin rash, nausea, vomiting, constipation, or diarrhea that can be controlled with treatment) before start of next cycle. If recovery is >29 days (Day 1 of the next cycle), patient must be withdrawn from study treatment.

If moderate or severe heart valve toxicities are observed, or the patient develops aneurysms of the great vessels of the heart, the patient must immediately be discontinued from the treatment and the toxicity reported to sponsor within 24 hours (see references on the ECHO assessment based on the Guidelines of the American and European Societies of Cardiac Echocardiography). If the patient develops new cardiovascular lesions in the chest, an MRI or CT with contrast of the abdomen should be performed to evaluate for development of abdominal vascular lesions. Exceptions to this rule must be approved by the IRBs and sponsor.

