5.6 Duration of Follow Up

Patients will be followed with follow-up visits monthly for the first three months after completing therapy then annually for 5 years with physical exam, performance status evaluation, labs and Echocardiography and Doppler (see study calendar, section 5.10).

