8.3 Reporting Serious Adverse Events

All new SAEs and Medical Events of Interest occurring during the study or within 45 days of the last administration of LY2157299 will be reported as long as the patient has not withdrawn consent. The principal investigators are responsible for reporting SAEs to the IRB and the FDA (21 CFR §312.32] or other applicable regulatory authority. The principal investigator is responsible for submitting follow-up reports for all SAEs regarding the patient's subsequent course until the SAE has resolved or until the patient's condition stabilizes (in the case of persistent impairment), or the patient dies.

Institution and Investigator understand and agree that Investigator and Institution are obligated under applicable law and regulations to report any serious and related adverse event, if any that occurs during treatment with the Product to the Institution's IRB/Ethics Committee and to the governing regulatory authority in accordance with applicable filing timelines promptly after any such event occurs. Investigator, within 24 hours (US) or one business day (EU) of first knowledge of such serious and related adverse event, will notify Lilly's assigned medical Monitor.

Prior to or at the time of filing any such report with the governing regulatory authority, the Investigator will also transmit an information copy of the report as sent to the authorities to Lilly.

IND # 126952

Protocol # 1505016222
Version Date 04/21/2017

The Investigator shall make available to Eli Lilly promptly such records as may be necessary and pertinent to investigate any such expedited adverse event, if specifically requested by Lilly.

Furthermore, the Investigator will inform Eli Lilly of the following:

- any events that result in protocol amendments for safety reasons, as well as any safety related regulatory action such as a clinical hold of the Research
- any pregnancies occurring in patients who are exposed to the Product in connection with the Research.
- In addition, the Investigator shall notify Lilly within 24 hours (US) or one business day (EU) of first knowledge of any Product complaints (communication of dissatisfaction that alleges deficiencies related to the identity, quality, durability, effectiveness, safety, labeling, purity, stability, and appearance).

The Investigator will also inform Eli Lilly within 1 business day of becoming aware of any actions from any authority that may affect the performance of the Research

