Medical Events of Interest

For reporting purposes, the Investigator will make note of any medical events of interest that occur during the treatment period.

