12.3 Data Management

All patient data will be entered and maintained using REDCAP, CTSC data management system. These data include clinical data and all patient safety data. The REDCap provides audit trails that track creation and modification of records that include user id and timestamp. Depending on the database account privileges, the data managers may be able to correct a discrepancy or if not, route it to the project data manager at WCM who can take appropriate action to correct the problem. Data clarification forms can also be printed out when necessary to be sent to the project data manager at JCTO.

The Nurse practitioner will also be documenting adverse events in EPIC during every follow up visit, All Adverse Events are captured in REDCap database and a report will be sent to Data safety monitoring board during their quarterly review meetings.

All key end points will be source verified by a second person at each site and errors will be corrected. Once the data is verified and all discrepancies are closed, the data can be locked/frozen. Locking and freezing can be done at different granular levels and will follow institutional SOPs and any specific requirements for the project.

Security measures that will be taken in order to protect patient data will include firewall technology and database level security which will be achieved by assigning roles and privileges to different levels of users and by requiring that the users authenticate themselves using user id and password. Additional security for data transfer between remote clients and servers will be achieved by using digital certificates/SSL. All data will be backed-up to tape periodically according to the Institutional SOPs. All data will be stored for at least 5 years following the termination of this study.

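### The protocol gives conflicting periods for collecting adverse events, so it is unclear whether new events found at the scheduled post-treatment visits are recorded and reported

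*Combined protocol and SAP*

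**What the plan says.** All references are to the combined protocol and SAP.

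- **Section 5.3, item 6:** "Adverse events evaluated and recorded using the NCI CTCAE version 4.0 throughout the treatment period (weeks 0-15". The adverse-event row of the section 5.10 calendar also appears to stop at week 15, although the table is hard to read as extracted.
- **Section 8.3:** "All new SAEs and Medical Events of Interest occurring during the study or within 45 days of the last administration of LY2157299 will be reported", provided the patient has not withdrawn consent.
- **Medical Events of Interest paragraph, after 8.3:** "the Investigator will make note of any medical events of interest that occur during the treatment period".
- **Section 5.6:** visits are monthly for three months after therapy, "then annually for 5 years with physical exam, performance status evaluation, labs and Echocardiography and Doppler".
- **Section 12.3:** "The Nurse practitioner will also be documenting adverse events in EPIC during every follow up visit". The same sentence says that all adverse events are captured in REDCap.
- **Sections 8.1.1 and 8.2:** all adverse events go on a patient log, and events after any dose are followed to resolution. Neither section has an end date.
- **Section 5.3, closing text:** moderate or severe valve toxicity, or aneurysm of the great vessels, is reported to the sponsor within 24 hours. The rule is tied to stopping treatment.
- **Section 11.1.1:** the primary safety endpoint is lack of grade 4 toxicity, with no end date.

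**The concern.** Staff who follow section 5.3 stop recording new adverse events at week 15. Staff who follow section 12.3 continue for years. Medical events of interest have one period in section 8.3 and another in the paragraph after it. With two enrolling sites, the safety data could differ by site for reasons unrelated to the patients.

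Cardiovascular findings are the most exposed. Section 2.2.3 reports that "daily dosing of LY2157299 resulted in dose-progressive incidence of vascular degeneration to the base of the aorta in dogs and rats", with aneurysms and deaths in rats, and gives the animal cardiac findings as the reason for cardiac monitoring. Section 5.6 then schedules echocardiography after treatment. Under a literal week-15 rule, a new aortic or valve abnormality on one of those scans would have no clear route into the adverse-event record. The same applies to late effects at the two irradiated lesions. The study-level rule in section 12.2, which counts Grade 3 and above non-hematological toxicities over 3 months, also depends on what is collected.

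**Working it through.** The plan states no figure to reproduce. The check is calendar arithmetic.

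**Inputs**
- Dosing is 14 days on and 14 off, marked in the calendar at weeks 1-2, 5-6, 9-10 and 13-14 (section 5.10).
- Adverse-event recording runs to week 15 (5.3). The serious-event limit is 45 days after the last dose (8.3).
- Post-treatment visits: 3 monthly + 5 annual = 8 (5.6).
- Assumptions: day 1 is the first dose, all four cycles are given, and a month is 28 to 30.4 days.

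**Window ends**
- Cycle starts: days 1, 29, 57 and 85. Last dose: 85 + 13 = day 98.
- End of week 15: 15 × 7 = day 105, which is 105 − 98 = 7 days after the last dose.
- 45-day limit: 98 + 45 = day 143.

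**Visit days.** The text does not fix the point from which monthly visits are counted, so four anchors were tried. Each visit day is anchor + k × month, for k = 1, 2, 3.

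| Anchor | Month 1 | Month 2 | Month 3 | Visits by day 105 | Visits by day 143 |
|---|---|---|---|---|---|
| Last dose, day 98 | 126-128 | 154-159 | 182-189 | 0 of 8 | 1 of 8 |
| Start of week 15, day 99 | 127-129 | 155-160 | 183-190 | 0 of 8 | 1 of 8 |
| End of week 15, day 105 | 133-135 | 161-166 | 189-196 | 0 of 8 | 1 of 8 |
| End of week 15 + 8 days, day 113 | 141-143 | 169-174 | 197-204 | 0 of 8 | 1 of 8, or 0 with a 30.4-day month (113 + 30.4 = 143.4) |

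The earliest annual visit is about day 98 + 365 = 463, beyond both limits. So 7 or 8 of the 8 visits fall outside both.

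**Sensitivity**
- Echocardiography only at the annual visits: 5 of 5 outside.
- Drug stopped after cycle 2 or 3, with visits timed from the last dose: 2 of 8 (cycle 2) or 1 of 8 (cycle 3) fall inside at least one window.
- Section 12.3 governs, or *during the study* includes follow-up: 0 of 8 outside.

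**Week-15 visit.** Its nominal range is days 99-105 and the calendar allows 8 days either way. The earliest dates are therefore 99 − 8 = 91 to 105 − 8 = 97, which is 1 to 7 days before the last dose on day 98. Section 5.5 treats a patient who has completed that visit as having completed treatment, so the allowance and section 5.5 do not fit together.

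**The case against.** A reader might infer that adverse events are collected only to week 15, serious events only to 45 days, and that later findings never reach the database. The documents do not support that.

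- Section 8.3 covers events *during the study* **or** within 45 days. Joined that way, the 45 days can extend the period instead of capping it.
- It is also tempting to argue that the 45-day clause would be pointless if the study included follow-up. It would not. Section 5.7 allows patients to be removed from both treatment and follow-up, for example for ineligibility or non-compliance, and such a patient may still be within 45 days of a dose.
- Section 12.3 provides for documentation at follow-up visits and capture in REDCap. Sections 8.1.1 and 8.2 set no end date.
- Section 5.3 describes on-study evaluations and does not forbid later recording. A longer period for serious than for non-serious events is not in itself a contradiction.
- Missing non-serious grade 1-3 events after week 15 would not alter the grade 4 endpoint.
- That the long echocardiography schedule exists to detect aortic damage is an inference. Section 2.2.3 speaks of monitoring patients on the drug.

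These points stand, and they rule out the strong reading. They do not settle which period applies. The protocol summary describes participation as 16 weeks and mentions annual follow-up separately, which favours the narrow reading of *during the study*. Section 12.3 does not say which visits count as follow-up, and the same passage still refers to quarterly board reviews where section 12.1 says annual, so it is a weak basis for overriding an explicit week limit. Section 8.2 can be read as following known events, not looking for new ones. Whether the 24-hour rule for valve toxicity and aneurysm applies after treatment is not stated. The mismatch over medical events of interest remains unless the study period and the treatment period are the same.

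**Conclusion.** The concern holds as an internal inconsistency. Depending on which passage is followed, between none and all of the 8 post-treatment visits fall outside the safety-collection period. Under the explicit week-15 and 45-day limits the figure is 7 or 8 of 8, or 5 of 5 if echocardiography is annual only. These counts assume four full cycles, months of 28 to 30.4 days and five annual visits. Section 5.6 leaves open whether echocardiography is done at the monthly visits.

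The consequence is conditional: a new aortic or valve finding at follow-up *might* not be recorded as an adverse event. The documents do not show that it would be lost. This should be corrected because it concerns data for a primary objective, but it is a clarification and does not invalidate the design.

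**What to change.** Reconcile section 5.3 item 6, the section 5.10 calendar, section 8.3, the medical-events paragraph and section 12.3 into one safety window:

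1. Define *during the study*, saying whether it includes the monthly and annual follow-up.
2. Record all new adverse events to at least 45 days after the last dose, which matches the limit already in section 8.3, and use the same period for medical events of interest.
3. State that new valve, aortic or large-vessel findings, and related serious events, found at the already scheduled follow-up visits are recorded and reported. Say whether the 24-hour rule in section 5.3 applies after treatment, and at which follow-up visits echocardiography is done.
4. State that the week-15 safety assessment takes place after the last dose, so that the 8-day allowance agrees with section 5.5.

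The cost is protocol wording and an adverse-event form at visits already planned, where section 12.3 already has staff documenting events. There are no new visits or procedures. The downside is slightly more data entry and a less favourable adverse-event count.
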